11.2 Serious Adverse Event (SAE)

An SAE is defined as any AE occurring that results in any of the following outcomes:

1. Death
2. A life-threatening adverse experience
3. An inpatient hospitalization or prolongation of existing hospitalization
4. A persistent or significant disability/incapacity
5. A congenital anomaly/birth defect
6. Required Intervention to Prevent Permanent Impairment or Damage

Emergency room visits that do not result in admission to the hospital should be evaluated for one of the other serious outcomes (e.g., life-threatening; required intervention to prevent permanent impairment or damage; other serious medically important event).

Other important medical events may also be considered an SAE when, based on appropriate medical judgment, they jeopardize the subject or require intervention to prevent one of the outcomes listed.

11.3 Serious Adverse Event Reporting

Study sites will document all SAEs that occur (whether or not related to study device). The collection period for all SAEs will begin after device is implanted and ends at Subject Exit.

In accordance with the standard operating procedures and policies of the local Institutional Review Board (IRB), the site investigator will report SAEs to the IRB within timeframe required. Please notify Grace Medical within 5 working days.

11.4 Unanticipated Adverse Device Effects

If an SAE is also an unanticipated adverse device effect, the investigator must submit to Grace Medical (within 3 business days) and reviewing IRB a report but within 10 working days.

12 DISCONTINUATION AND REPLACEMENT OF SUBJECTS

12.1 Early Discontinuation

A subject may be discontinued from study treatment at any time if the subject, the investigator, or the Sponsor feels that it is not in the subject's best interest to continue. The following is a partial list of possible reasons for study treatment discontinuation:

1. Subject withdrawal of consent (or assent)
2. Lost to or refused follow-up
3. Adverse Event or Serious Adverse Event if investigator feels that it is in the best interest of the patient.

If a subject is withdrawn from treatment due to an adverse event, the subject will be followed and treated by the Investigator until the abnormal parameter or symptom has resolved or stabilized.

All subjects who discontinue study treatment should come in for an early discontinuation visit as soon as possible and then should be encouraged to complete all applicable remaining scheduled visits and procedures.

All subjects are free to withdraw from participation at any time, for any reason, specified or unspecified, and without prejudice.

Reasonable attempts will be made by the investigator to provide a reason for subject withdrawals. The reason for the subject's withdrawal from the study will be specified in the subject's source documents.

12.2 Withdrawal of Subjects from the Study

A subject may be withdrawn from the study at any time if the subject, the investigator, or the sponsor feels that it is not in the subject's best interest to continue.

The reason for the subject's withdrawal from the study will be specified in the subject's source documents as well as Study Exit Form

12.3 Replacement of Subjects

Subjects who withdraw from the study may be replaced up to a total of 15 for the site.

13 PROTOCOL DEVIATIONS

A protocol deviation occurs when the subject, investigator, or Sponsor fails to adhere to significant protocol requirements affecting the inclusion, exclusion, subject safety and primary endpoint criteria. Protocol deviations for this study include, but are not limited to, the following:

1. Failure to Obtain Informed Consent
2. Failure to meet inclusion/exclusion criteria (Eligibility)
3. Failure to maintain study evaluation time frames for follow-up visits

Failure to comply with Good Clinical Practice (GCP) guidelines will also result in a protocol deviation. The Sponsor will determine if a protocol deviation will result in withdrawal of a subject.

When a protocol deviation occurs, it will be discussed with the investigator and a Protocol Deviation Form detailing the deviation will be completed. This form will be signed by a Sponsor representative and the Investigator. A copy of the form will be filed in the site's regulatory binder and in the Sponsor's files.

Protocol deviations should also be reported as required to the site's IRB.

14 STATISTICAL METHODS AND CONSIDERATIONS

As this study is for safety and utilizing a small number of subjects, no statistical analysis will be completed. Information will be presented to the FDA in tabular format.

Adverse event rates will be coded by body system will include the number of patients for whom the event occurred, the rate of occurrence, and the severity and relationship to study device.

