RATIONALE	This investigational clinical study is to assess the safety of Tympanoseal, a sodium/calcium alginate tympanic membrane perforation device that acts as a scaffold during the healing process. It is intended for use following removal or extrusion of indwelling tympanostomy tubes or traumatic injury of the tympanic membrane.
STUDY DESIGN	This is a non-randomized, non-blinded study.
PRIMARY OBJECTIVE	The purpose of this investigational study is to assess the safety of Tympanoseal when used during the healing process.
SECONDARY OBJECTIVES	Determine if any adverse events occur during presence of material on tympanic membrane.
NUMBER OF SUBJECTS	Up to 15 at each site
SUBJECT SELECTION CRITERIA	
Inclusion Criteria:
 
1) Male or female patients over 2 years of age at enrollment 2) Documentation of a retained tympanostomy tube or persistent perforation less than 5 mm. 3) Written informed consent (and assent when applicable) obtained from subject or subject's legal guardian and ability for subject to comply with the requirements of the study
 
Exclusion Criteria:
 
1) Active otorrhea or otitis media 2) History of cholesteatoma 3) Perforations on the edge of the tympanic membrane 4) Presence of a condition or abnormality that in the opinion of the Investigator would compromise the safety of the patient or the quality of the data 5) Subject is taking systemic/oral corticosteroids 6) Subject will require the continued use of any type of topical otic medication to the ear(s) with Tympanoseal.

RESEARCH PRODUCT	Tympanoseal will be placed during a surgical procedure.

DURATION OF SUBJECT PARTICIPATION AND DURATION OF STUDY	
Subjects may be in study for up to 36 weeks. Subjects may exit study at any follow-up visit if healing is noted by investigator.
 
It is expected that there will be up to 3 follow-up visits after surgery:
 
 4 weeks (\pm 7 days) 10 weeks (\pm 7 days) 16 weeks (\pm 14 days) 
However, additional follow-up visits may be scheduled (until no product remains visible) at 20 weeks (\pm 14 days), 24 weeks (\pm 14 days), 30 weeks (\pm 14 days), 36 weeks (\pm 14 days). Subjects may exit study at any interval after Tympanoseal device is no longer present. Additional visits may also be scheduled per investigator discretion.
 
Estimated total duration of the study is expected to be 18 months from subject recruitment to final subject follow-up.

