CONCOMITANT MEDICATIONS	
Prohibited:
 
 Chronic systemic/oral corticosteroids Topical medications for the ear unless medically necessary
EFFICACY EVALUATIONS	Otomicroscopy with photograph of tympanic membrane at each Follow-Up Visit until Study Exit
PRIMARY ENDPOINT	Healing of Tympanic Membrane
SECONDARY ENDPOINTS	Resorption of Tympanoseal
SAFETY EVALUATIONS	Examination during follow-up visits will establish an incidence of adverse events to the implantation of Tympanoseal
PLANNED INTERIM ANALYSES	Due to short time-frame of this study, no interim analyses are planned. Serious adverse events will be monitored on an ongoing basis throughout the study.
STATISTICS	As this study is for safety and utilizing a small number of subjects, no statistical analysis will be completed. Information will be presented to the FDA in tabular format.
RATIONALE FOR NUMBER OF SUBJECTS	Suggested by the FDA during pre-510(k) conference call.

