3 STUDY OBJECTIVES

3.1 Primary Objective

The primary objective is to assess the safety of Tympanoseal when used as scaffolding during the healing process.

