3.2 Secondary Objectives

The secondary objective is to determine ability / if any adverse events arise from implantation of Tympanoseal such as colonization by microorganisms or diminution of hearing by damping of tympanic membrane vibrations.

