5 CRITERIA FOR EVALUATION

5.1 Primary Efficacy Endpoint

The primary endpoint will be the healing of the tympanic membrane perforation. In chinchillas this occurred between 1 and 2 months.

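### Both objectives are safety, but the ranked endpoints are healing and resorption, and no precision is planned for the adverse event rates that answer the primary objective

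*Protocol*

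**What the plan says.** **Objectives.** The synopsis gives the primary objective as "The purpose of this investigational study is to assess the safety of Tympanoseal when used during the healing process", and Section 3.1 agrees: "The primary objective is to assess the safety of Tympanoseal when used as scaffolding during the healing process". The synopsis secondary objective is "Determine if any adverse events occur during presence of material on tympanic membrane". Section 3.2 has "The secondary objective is to determine ability / if any adverse events arise from implantation of Tympanoseal", in which the word before the slash is never completed.

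**Endpoints.** The synopsis row for the primary endpoint reads "Healing of Tympanic Membrane", and the secondary row names resorption. Section 5.1 is headed as an efficacy endpoint, but its text is unqualified: "The primary endpoint will be the healing of the tympanic membrane perforation". Section 5.2, also headed as efficacy, makes full resorption at 16 weeks the secondary endpoint. AE incidence appears in the synopsis and in Section 5.3 under safety evaluations, with no rank.

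**Analysis.** The synopsis and Section 14 both state: "As this study is for safety and utilizing a small number of subjects, no statistical analysis will be completed". Results go to the FDA as tables. Section 14 then says that the AE reporting will give "the number of patients for whom the event occurred, the rate of occurrence, and the severity and relationship to study device". Section 14.1 sets the size at up to 30 subjects, a number reached in discussion with the FDA. The protocol mentions no interval or other measure of precision.

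**The concern.** Two things do not fit together.

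First, the outcome labelled primary does not answer the primary objective, and the outcome that does answer it has no place in the endpoint ranking. Conversely, healing and resorption are ranked but have no stated objective. Sections 1 and 2 describe scaffold function as a purpose, but Section 3 does not carry this through. The label also has an operational effect, because Section 13 defines protocol deviations partly by reference to the primary endpoint criteria.

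Second, the two reasons given for doing no statistical analysis (the study is about safety, and it is small) do not justify leaving out precision. An AE rate is an estimate, and a small sample is where its uncertainty is largest. What is at stake is a table showing few or no events that is read as stronger evidence of safety than 30 subjects can give.

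**Working it through.** **1. Objectives against endpoints**

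| Level | Stated objective | Stated endpoint |
|---|---|---|
| Primary | Safety (synopsis, 3.1) | Healing (synopsis, 5.1) |
| Secondary | Occurrence of AEs (synopsis, 3.2) | Resorption (synopsis, 5.2) |
| Unranked | none | AE incidence (synopsis, 5.3) |

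Neither ranked row matches. AE incidence, which would answer both objectives, is in the unranked row.

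**2. Sample size.** Section 4 gives two sites with at most 15 subjects each: 2 × 15 = 30, which agrees with Section 14.1. The protocol gives no event rate, margin, power or confidence level, so there is no statistical calculation to reproduce.

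**3. Precision of an AE proportion.** Inputs: n = 30 (overall ceiling) and n = 15 (ceiling for one site). The two-sided 95% level and the event counts are assumptions for illustration. The method is the exact Clopper-Pearson interval for the proportion of subjects with at least one AE.

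- Zero events: the upper limit solves (1 − p)^n = 0.025, so p = 1 − 0.025^(1/n).
  - n = 30: 1 − 0.025^(1/30) = 1 − 0.8843 = 0.1157, or **11.6%**.
  - n = 15: 1 − 0.025^(1/15) = 1 − 0.7820 = 0.2180, or **21.8%**.
- One event in 30 (observed 3.3%):
  - The lower limit is 1 − 0.975^(1/30) = 0.0008.
  - The upper limit is the 0.975 quantile of Beta(2, 29) = 0.1722.
  - The interval is **0.1% to 17.2%**.

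**4. How easily a true risk gives an empty row.** The chance of seeing no events in 30 subjects is (1 − p)^30. For a true rate of 5% it is 0.95^30 = 0.215. For a true rate of 2% it is 0.98^30 = 0.545. A bare zero in the table would show none of this.

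**5. Points that the intervals depend on**

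- *Unit.* Section 4 allows implantation in both ears and Section 8.4 uses one device per membrane. Healing and resorption can therefore arise twice in one subject, and an exact binomial interval computed over ears would ignore the correlation within a subject.
- *Follow-up.* Sections 10.4 to 10.7 let a healed subject leave from week 4, while others may stay to week 36. AE proportions therefore mix unequal observation times.
- *Start of AE collection.* Section 9.1.7 starts at the procedure date and Section 11.1 starts after implantation. These differ by at most part of one day, but an event during the operation before implantation counts under one and not under the other.

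**The case against.** The strongest reply is that the sentence excluding statistical analysis should be read with what follows it. Section 14 goes straight on to tables, patient counts and rates, so the natural meaning is that no inferential testing is planned. A reader can also work out an interval from the counts. Much of this stands. A reader might infer that the protocol contradicts itself outright, or forbids any interval. The text does not support that: it is a tension in wording, open to the milder reading. But on the milder reading, too, no precision is planned for the main result. Nor can the point be left to an analysis plan that is not shown, because the protocol does not defer the analysis to one; it states a rule.

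A second reply is that rank matters little without a test or success criterion, that Section 5.3 makes AE incidence a criterion of its own, and that it is the only outcome with a reporting specification in Section 14. This also stands in part. It would be wrong to infer that safety goes unevaluated or that AEs are not collected. The defect is in the labelling and in the link between objectives and endpoints.

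A third reply is that the FDA suggested the sample size. That supports the number of subjects, which is not challenged here. The protocol does not say that the FDA asked for an efficacy primary endpoint or for rates without intervals.

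**Conclusion.** The point holds as a mismatch between objectives and ranked endpoints, together with AE rates planned without precision. Its size is set by the sample: at best, no events in 30 subjects leaves a true rate of up to 11.6% possible. The limit is 21.8% with 15 subjects, and one event in 30 gives 0.1% to 17.2%. These figures assume one outcome per subject, independent subjects, a two-sided 95% level and, for the first and last, full enrolment. Thirty is a maximum, so fewer subjects would give less precision.

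It does not follow that the study is infeasible or too small for its purpose. Nor should the healing fractions from the chinchilla study in Section 1.1 be used to project precision for healing in this trial. That study reports three different fractions for three groups of animals, and none of them bears on an AE rate in human subjects.

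The change is a cheap improvement that should be made.

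**What to change.** 1. **Endpoints and objectives.**
   - In the synopsis and Section 5, name the proportion of implanted subjects with at least one AE as the primary safety endpoint.
   - Show the same proportion for device-related AEs, and state which of the relationship categories in Section 11.1 count.
   - Call healing the primary efficacy endpoint in the synopsis row and in the text of 5.1, as the 5.1 heading already does.
   - Complete the unfinished phrase in Section 3.2 so that healing and resorption have a stated objective.
2. **Analysis statement.** In the synopsis and Section 14, replace the sentence excluding statistical analysis with: *No hypothesis tests are planned; subject-level AE, healing and resorption proportions will be shown with exact (Clopper-Pearson) 95% confidence intervals.*
   - For bilateral cases, define healing and resorption at subject level. If they are reported per ear, use a method that allows for correlation within a subject.
   - Show the duration of follow-up beside the AE rates, because exit can fall anywhere from week 4 to week 36.
3. **Sample size.** In Section 14.1, state the precision at 30 subjects (no events: upper limit 11.6%) and that it is worse if fewer enrol.
4. **Minor.** Reconcile Sections 9.1.7 and 11.1 on when AE collection starts.

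The cost is wording in the synopsis and Sections 3.2, 5, 14 and 14.1, one reconciled sentence on AE collection, and added columns in tables already planned. The one downside is that the safety result will look less favourable because its uncertainty is visible.

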14.1 Sample Size and Randomization

Up to 30 subjects will be enrolled in this non-randomized study. The number of subjects was determined by discussion with the FDA.

15 DATA COLLECTION, RETENTION AND MONITORING

15.1 Data Collection Instruments

The Investigator will prepare and maintain adequate and accurate source documents designed to record all observations and other pertinent data for each subject treated with the study device.

Study personnel at each site will enter data from source documents corresponding to a subject's visit into the Case Report Forms (CRFs) provided when the information corresponding to that visit is available. Subjects will not be identified by name in the study database or on any study documents to be collected by the Sponsor (or designee), but will be identified by subject number and initials.

If any correction is made on a CRF, the study staff member will line through the incorrect data, write in the correct data and initial and date the change.

The Investigator is responsible for all information collected on subjects enrolled in this study. All data collected during the course of this study must be reviewed and verified for completeness and accuracy by the Investigator. Copies of the completed CRFs will remain at the Investigator's site at the completion of the study.

15.2 Availability and Retention of Investigational Records

The Investigator must make study data accessible to the monitor, other authorized representatives of the Sponsor (or designee), IRB, and Regulatory Agency (e.g., FDA) inspectors upon request. A file for each subject must be maintained that includes the signed Informed Consent, HIPAA Authorization and Assent Form and copies of all source documentation related to that subject. The Investigator must ensure the reliability and availability of source documents from which the information on the CRF was derived.

All study documents (patient files, signed informed consent forms, copies of CRFs, Study File Notebook, etc.) must be kept secured for a period of two years following marketing of the investigational product or for two years after centers have been notified that the study has been discontinued. There may be other circumstances for which the Sponsor is required to maintain study records and, therefore, the Sponsor should be contacted prior to removing study records for any reason.

15.3 Monitoring

Grace Medical, Inc. will serve as the sponsor of this investigational clinical study. It is the responsibility of the sponsor of this clinical study to ensure proper monitoring to see that the study is conducted in full compliance with the study protocol in conformance to Title 21, Code of Federal Regulations (CFR) Parts, 50, 54, 56, and 812, Guidelines for the Monitoring of Clinical Investigations and the Declaration of Helsinki, as amended. The study will be monitored by a Clinical Research Associate or designee of Grace Medical (Clinical Monitor).

By signing this protocol, the Investigator grants permission to the Sponsor (or designee), and appropriate regulatory authorities to conduct on-site monitoring and/or auditing of all appropriate study documentation.

15.3.1 SITE INITIATION VISIT

Once all regulatory documents and approval are received, a site initiation visit will be scheduled. During this visit, the Monitor will review the following with the Principal Investigator and his/her staff as appropriate:

1. Study goals and obligations
2. Protocol procedures (with particular attention to inclusion/exclusion criteria, enrollment goals, adverse events, primary efficacy variables and GCP compliance)
3. Informed consent procedure
4. AE/SAE reporting
5. CRF completion and error correction/need for adequate source documentation
6. Maintenance of the investigator binder and site visit log
7. Investigational status of test article and requirements for accountability
8. Any other issue as deemed important to the conduct of the study

At this time, the following documents will be obtained if not already forwarded to Grace Medical:

1. Copy of IRB/EC approval letter
2. Copy of IRB/EC approved informed consent document
3. Signed Clinical Trial Research Agreement
4. Curricula vitae and Medical Licenses for the Principal Investigator and each Sub-Investigator
5. Financial Disclosure Form

15.3.2 INTERIM MONITORING VISITS

The first interim monitoring visit at each site will be made after the majority of subjects have completed the four week follow-up visit unless it is determined that a visit should be made earlier. The Clinical Research Associate or designee will maintain personal contact with the Investigator(s) and study personnel by telephone, mail, email and on-site visits. The Clinical Research Associate or designee will require access to all subject and study records in order to verify that:

1. Informed consent has been obtained for each subject
2. The site is in compliance with the study protocol
3. Source documentation and CRF completion
4. Study administration records are complete
5. Product inventory is verified and accurate

The Study Site Documentation Binder will also be reviewed. Additional monitoring visits will be scheduled as appropriate.

15.3.3 FINAL MONITORING VISIT

At the close of the study, the Clinical Research Associates or designee will conduct a final visit to conduct the following:

1. Collect outstanding data
2. Insure the completeness of study files
3. Review record retention requirements with study personnel
4. Provide for disposition of any remaining study supplies and devices.

15.3.4 STUDY SITE DOCUMENTATION BINDER

The Study Coordinator at each site will be trained on the proper maintenance of the Study Site Documentation Binder (Regulatory Binder). Correspondence, agreements, and logs are to be kept up-to date and copies should be forwarded to the Sponsor in a timely fashion.

The contents of the Study Site Documentation Binder may include but are not limited to:

1. Clinical Trial Research Agreement / contract
2. Financial Disclosure Forms
3. IRB Approval & Correspondence
4. IRB Approved Consent Form
5. Investigator CVs (signed & dated)
6. Training / Meeting Log
7. Signature Log
8. Device Log
9. Screening Log
10. Patient Enrollment Log
11. Sponsor Monitoring Log
12. Study Communication

